Appendix H RESPONSE CRITERIA FOR MULTIPLE MYELOMA
Summary of International Myeloma Working Group Uniform Response Criteria
(IMWG-URC)

Response Subcategory^a	Response Criteria
sCR ^b	
 • Negative immunofixation on the serum and urine and • Disappearance of any soft tissue plasmacytomas and • < 5% plasma cells in bone marrow and • Normal SFLC ratio and • Absence of clonal cells in bone marrow^c
CR ^b	
 • Negative immunofixation on the serum and urine and • Disappearance of any soft tissue plasmacytomas and • < 5% plasma cells in bone marrow
VGPR ^{b, d}	
 • Serum and urine M-protein detectable by immunofixation, but not on electrophoresis or • $\geq 90\%$ reduction in serum M-component with urine M-component < 100 mg per 24 hours
PR ^{b, d}	
 • $\geq 50\%$ reduction of serum M-protein and reduction in 24-hour urinary M-protein by $\geq 90\%$ or to < 200 mg per 24 hours • If the serum and urine M-protein are not measurable, a decrease $\geq 50\%$ in the difference between involved and uninvolved FLC levels is required in place of the M-protein criteria. • If the serum and urine M-protein are not measurable, a decrease $\geq 50\%$ in the difference between involved and uninvolved FLC levels is required in place of the M-protein criteria. • If present at baseline, a $\geq 50\%$ reduction in the size of soft tissue plasmacytomas is also required^{d, e}
Stable disease	
 • Not meeting criteria for CR, VGPR, PR, or PD

Footnoted defined on next page

Summary of International Myeloma Working Group Uniform Response Criteria (IMWG-URC) (cont'd)

Response Subcategory ^a	Response Criteria

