PD ^c	
Any one or more of the following increase of $\geq 25\%$ from lowest response value in:
 
 • Serum M-component (absolute increase must be ≥ 0.5 g/dL) and/or • Urine M-component (absolute increase must be ≥ 200 mg per 24 hours) and/or • Only in subjects without measurable serum and urine M-protein levels: the difference between involved and uninvolved FLC levels (absolute increase must be > 10 mg/dL) • Only in subjects without measurable serum and urine M-protein levels and without measurable disease by FLC levels, bone marrow PC percentage (absolute percentage must be $\geq 10\%$) • Bone marrow plasma cell percentages (absolute % must be $\geq 10\%$) 
Definite development of new bone lesions or soft tissue plasmacytomas or definite increase in size of existing bone lesions or soft tissue plasmacytomas^{f, g, h}
 
Development of hypercalcemia (corrected serum calcium > 11.5 mg/dL or 2.65 mmol/L) attributed solely to the plasma cell proliferative disorder

Page 2 of 2

Sources: [Durie 2006](#); [Rajkumar 2011](#).

CR = complete response; sCR = stringent complete response; FLC = serum free light chain; PD = progressive disease; PR = partial response; SFLC = serum free light chain; VGPR = very good partial response.

^a Subjects with measurable disease in both serum (SPEP) and urine (UPEP) at study entry are required to meet response criteria in both UPEP and SPEP in order to qualify for a PR or better. Conversely, it should be noted that criteria for PD only need to be met and confirmed in 1 parameter.

^b **All response categories (CR, sCR, VGPR, PR) require 2 consecutive assessments** made at any time before the institution of any new therapy, as well as no known evidence of progressive or new bone lesions if radiographic studies were performed. Radiographic studies are not required to satisfy these response requirements. Bone marrow assessments are not required to be confirmed by repeat testing, but these should be done within 30 days of the confirmatory assessment if appropriate for the response category.

^c Presence/absence of clonal cells is based upon the κ/λ ratio. An abnormal κ/λ ratio by immunohistochemistry and/or immunofluorescence requires a minimum of 100 plasma cells for analysis. An abnormal ratio reflecting presence of an abnormal clone is κ/λ of $> 4:1$ or $< 1:2$.

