^d Response criteria for all categories and subcategories of response except CR and VGPR are applicable only to subjects that have “measurable” disease defined by at least one of SPEP ≥ 1.0 g/dL or UPEP ≥ 200 mg per 24 hours; except for assessment of sCR, CR, or VGPR, subjects with measurable disease restricted to SPEP will need to be followed only by SPEP. Correspondingly, subjects with measurable disease restricted to UPEP will need to be followed only by UPEP.

^e **Determination of PD based on M-protein, hypercalcemia, or FLC while on study requires 2 consecutive assessments** made at any time before classification of PD and/or the institution of new therapy. Serum M-component increases of ≥ 1 g/dL are sufficient to define progression if starting M-component is ≥ 5 g/dL.

^f Plasmacytomas: A definite increase in the size is defined as a $\geq 50\%$ increase as measured serially by the sum of the products of the cross-diameters of the measurable lesion. A plasmacytoma is considered measurable if the longest diameter is at least 1 cm and the product of the cross diameters is at least 1 cm^2 . Plasmacytomas of lesser size will be considered nonmeasurable.

^g The requirement for bi-directional measurements will only be applied to plasmacytomas.

^h The plasmacytoma specifications for PD are based on the sponsor’s interpretation of the IMWG-URC and practical considerations for study execution.

Definition of Minimal Response and Near-Complete Response per EBMT Criteria

Response Subcategory	Response Criteria
MR ^a	≥ 25 but < 49% reduction in serum M-protein and a 50-89% reduction in 24-hour urinary M-protein, which still exceeds 200 mg per 24 h
	For subjects with non-secretory myeloma only, 25-49% reduction in plasma cells in a bone marrow aspirate and on trephine biopsy, if biopsy is performed.
	25-49% reduction in the size of soft tissue plasmacytomas (by radiography or clinical examination)
	No increase in size or number of lytic bone lesions (development of compression fracture does not exclude response)
nCR ^a	Immunofixation-positive response. Absence of M-protein on electrophoresis, independent of the immunofixation test status, stable bone disease, and a normal serum calcium concentration,

Sources: [Bladé 1998](#), [Kyle 2009](#), [Richardson 2003](#).

EBMT = European Group for Blood and Marrow Transplantation; MR = minimal response; nCR = near- complete response.

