3.2 Secondary Endpoints

Phase 1b/2:

- Pharmacokinetics of OPZ tablet and OPZ ER tablet

Phase 2:

- Clinical benefit response status, to determine whether a subject has a best response of sCR, CR, nCR, VGPR, or PR, as defined by IMWG–URC and EBMT criteria (MR and nCR)
- Duration of response
- Progression–free survival
- Time to progression

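### Appendix H bounds minimal response above as well as below, so with serum and urine both measurable some deeper responses score as stable disease, which can only lower the secondary CBR

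*Protocol*

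**What the plan says.** Appendix H has two response tables.

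- **PR** (IMWG-URC table) is set by minimum reductions: a serum fall of at least 50%, "reduction of serum M-protein and reduction in 24-hour urinary M-protein by" at least 90% or to below 200 mg/24 h. Under footnote a, subjects with both components measurable are "required to meet response criteria in both UPEP and SPEP in order to qualify for a PR or better".
- **MR** (EBMT table) is set by bounded ranges: "≥ 25 but < 49% reduction in serum M-protein and a 50-89% reduction in 24-hour urinary M-protein", "which still exceeds 200 mg per 24 h". Separate rows cover non-secretory disease, lytic lesions and plasmacytomas, the last being "25-49% reduction in the size of soft tissue plasmacytomas".
- **Stable disease** is the residual class: "Not meeting criteria for CR, VGPR, PR, or PD".
- **Single-component disease** is covered by footnote d of the IMWG-URC table: "subjects with measurable disease restricted to SPEP will need to be followed only by SPEP", and likewise for urine.

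Inclusion criterion 1 (protocol 4.1) admits subjects measurable only by FLC. Appendix H gives them a PR rule but no MR rule.

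CBR is ORR plus MR (protocol 2.2, SAP 2.2.2). Duration of clinical benefit runs from the first MR or better (SAP 7.5.5). The investigator assesses response (protocol 7.6).

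**The concern.** A response scale should not rank a deeper response below a shallower one. Here PR has no ceiling but MR does, and the serum and urine conditions are joined by an and. A subject can exceed the MR range on one component, miss PR on the other, and satisfy neither definition. Nothing in Appendix H or the SAP says that such a subject is MR, so the residual class takes them.

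The secondary CBR and its duration are at stake. Because investigators assess response, one may apply the ranges literally and another may treat them as minimum reductions. CBR would then depend partly on who did the reading.

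**Working it through.** **The plan's own figure.** The documents give no design figure for CBR or MR. The nearby figure is the ORR test (protocol 10.2, SAP 2.3). An exact binomial with n = 46 and rejection at 12 or more responders gives power 76.7% at ORR 30% (stated: 77%) and type I error 3.5% at 15%. A cut-off of 11 would give 7.4%, so 12 is the smallest valid cut-off. MR does not enter this rule, so nothing below changes it.

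**The rules as written.** Let s and u be the percentage falls in serum and urine M-protein, B the baseline urine M-protein in mg/24 h, and R = B × (1 − u/100) the residual. Both components are measurable, changes are confirmed, there is no PD, and other MR conditions are met.

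- PR: s ≥ 50 and (u ≥ 90 or R < 200)
- Literal MR: 25 ≤ s < 49 and 50 ≤ u ≤ 89 and R > 200
- MR as minimum reductions: s ≥ 25 and u ≥ 50, PR not met
- Otherwise: SD

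| B | s | u | R | Literal | As minimum |
|---|---|---|---|---|---|
| 2000 | 30% | 60% | 800 | MR | MR |
| 2000 | 60% | 60% | 800 | SD | MR |
| 2000 | 60% | 85% | 300 | SD | MR |
| 2000 | 30% | 92% | 160 | SD | MR |
| 1000 | 30% | 60% | 400 | MR | MR |
| 1000 | 30% | 85% | 150 | SD | MR |
| 1000 | 49.5% | 60% | 400 | SD | MR |
| 400 | 30% | 60% | 160 | SD | MR |

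**Reversed order.** At B = 2000, rows 2 to 4 are each at least as deep as row 1 on both components and deeper on at least one, yet they score lower. Row 6 against row 5 shows the same at B = 1000.

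**Low urine baseline.** If B ≤ 400 and u ≥ 50, then R ≤ B/2 ≤ 200, so R > 200 fails. With s from 25% to below 49%, PR fails as well, and no urine result gives MR. Protocol 4.1 counts urine M-protein as measurable from 200 mg/24 h, so such subjects can be enrolled.

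**Serum boundary.** From s = 49% to below 50%, neither MR nor PR applies. Rounding to whole percentages does not help, because 49% itself is excluded. The plasmacytoma and non-secretory rows run to 49% inclusive.

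**Direction.** Any (s, u) inside the literal MR range also has s ≥ 25 and u ≥ 50 and, since s < 49, is not PR. The literal MR set is therefore contained in the minimum-reduction set, and CBR under literal use can only be equal or lower.

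**Size per subject.** 1/46 = 2.2 points in the combined group; 1/40 = 2.5 points in the Phase 2 cohort alone. As an illustration, assume a literal count of 18/46 = 39.1% (exact 95% CI 25.1% to 54.6%). One, two or three reclassified subjects give 19/46 = 41.3%, 20/46 = 43.5% or 21/46 = 45.7%. The 18 is an assumption.

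**The case against.** The strongest reply is that the limits come from published EBMT criteria, which Appendix H cites and by which CBR is defined. Removing them would make MR study-specific. Whether the limits depart from the sources cannot be checked here. That stands as a reason to label the change, but it does not remove the reversal in the rule as printed. It is also fair to say that investigators may already read MR as a minimum, that CBR is estimated and not tested, and that the literal error is conservative.

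Three stronger readings are tempting and are not supported:

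- *That SAP 3.2 leaves MR out of clinical benefit.* The list "Clinical benefit response status, to determine whether a subject has a best response of sCR, CR, nCR, VGPR, or PR" omits it, but the same sentence goes on to name MR and nCR under the EBMT criteria. SAP 2.2.2, SAP 7.5.5 and protocol 10.1 also include MR.
- *That MR is unreachable in single-component disease.* Footnote d can reasonably be read to let these subjects be followed on one component. For serum-only disease that leaves just the gap from 49% to below 50%. The EBMT table does not carry the footnote, so its application to MR needs stating, but unreachability is not shown.
- *That the loss could be about 27 points.* Protocol Table 1 shows CBR 46.7% and ORR 20.0% for 2/7 tablets in Study 2011-001, a difference of 26.7 points. Treating that as the loss assumes every MR in a group of 15 disappears. That study's MR wording is not in the documents, and it was the single-agent study.

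**Conclusion.** The defect is real as the text stands, within limits. The reversed order arises when serum and urine M-protein are both measurable; the documents do not give that share. The low-baseline exclusion and the serum gap also follow directly from the text. The missing MR rule for FLC-only subjects is an omission whose effect depends on the rule adopted.

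The downward direction for CBR is certain only under literal application. The size is 2.2 points per affected subject at n = 46, and the number affected cannot be derived from the documents. Duration of clinical benefit is affected too: a subject never scored MR or better drops out of it, and one who later reaches PR starts the clock later. The net effect on the median is not predictable. ORR, the 12-of-46 rule and its 77% power do not change.

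**What to change.** In Appendix H, state that a subject is MR if the serum fall is at least 25% and the urine fall at least 50%, each applied only to a component measurable at baseline, and neither PR nor PD is met. Remove the upper limits and the residual-urine condition. Keep the plasmacytoma, lytic-lesion and non-secretory conditions, reading the plasmacytoma reduction as a minimum too.

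Also state:

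- that footnote d applies to MR;
- which serum measurability threshold governs: inclusion criterion 1 uses 500 mg/dL, footnote d uses 1.0 g/dL;
- how FLC-only subjects are classed for MR.

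The cost is wording in Appendix H and a re-derivation from values already collected. The downside is a study-specific reading of the cited criteria, which should be labelled as such. Because response was investigator-assessed and the Amendment 4 summary records the primary analysis as complete, replacing the result now would be post hoc. Report CBR and its duration under both the literal and the minimum-reduction rule, with the number of subjects who change class.

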4.1 INCLUSION CRITERIA

1. Diagnosis of multiple myeloma with measurable disease as indicated by 1 or more of the following:
 - a. Serum M-protein \geq 500 mg/dL
 - b. Urine M-protein \geq 200 mg/24 hour
 - c. Only for subjects without measurable serum and urine M-protein, serum free light chain: Involved free light chain (FLC) level \geq 10 mg/dL, provided serum FLC ratio is abnormal
2. Patients requiring therapy who have relapsed and/or are refractory to their last therapy and have been treated with at least 1, but not more than 5, lines of multiple myeloma

- therapy. Prior therapy must consist of at least 1 regimen that included lenalidomide and/or bortezomib. Patients should be considered to be appropriate candidates for a clinical study by their treating physicians. Relapsed patients must have previously achieved \geq MR on at least 1 line of therapy as assessed by the treating physician. Refractory patients are allowed, but it is not required that patients be refractory to their last therapy. Primary refractory patients are allowed in the Phase 1b portion of the study only.
3. Males and females \geq 18 years of age
 4. Eastern Cooperative Oncology Group Performance Status (ECOG PS) 0–2
 5. Adequate hepatic function, with bilirubin \leq 1.5 times the upper limit of normal (ULN) in the absence of Gilbert’s disease or hemolysis, aspartate aminotransferase (AST) \leq 3 times ULN, and alanine aminotransferase (ALT) \leq 3 times ULN
 6. Absolute neutrophil count (ANC) \geq 1000 cells/mcL, hemoglobin \geq 7.0 g/dL, and platelet count \geq 30,000 cells/mcL:
 - a. Patients must not have received platelet transfusions for at least 1 week prior to Screening.
 - b. Screening ANC must be independent of granulocyte colony-stimulating factor (G-CSF) and granulocyte-macrophage colony-stimulating factor (GM-CSF) support for at least 1 week and of pegylated G-CSF for \geq 2 weeks prior to first dose.
 - c. Patients may receive red blood cell (RBC) transfusions or receive supportive care with erythropoietin or darbepoetin in accordance with institutional guidelines.
 7. Calculated or measured creatinine clearance (CrCl) rate of \geq 30 mL/min calculated using the formula of Cockcroft and Gault $[(140 - \text{age}) \times \text{mass (kg)} / (72 \times \text{serum creatinine mg/dL})]$. Multiply result by 0.85 if female.
 8. Uric acid, if elevated, must be corrected to within laboratory normal range before dosing

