10.2 SAMPLE SIZE CONSIDERATIONS

For the Phase 1b portion of the study, it is estimated that approximately 60 subjects (approximately 30 subjects per treatment schedule) will be required to determine the recommended Phase 2 dose for each treatment schedule. This is based on an estimate that up to 5 cohorts will be enrolled per treatment schedule, with up to 6 evaluable subjects per cohort.

For the recommended dose group (dose-escalation cohort plus Phase 2 cohort), the null (H_0) and the alternative (H_A) hypotheses are as follows:

$$H_0: \text{ORR}_{\text{Cd}} \leq 15\% \quad H_A: \text{ORR}_{\text{Cd}} > 15\%$$

With a sample size of 46 subjects (6 evaluable dose-escalation subjects + 40 Phase 2 subjects enrolled at the recommended dose) per schedule, a 1-sample exact binomial test with a 1-sided significance level of 5% will have 77% power at an ORR of 30%. If at least 12 of the 46 subjects have a best overall response of PR or better, then the null hypothesis will be rejected and it will be inferred that the ORR is $> 15\%$.

The total study sample size will depend on the number of dose levels required to establish the recommended dose for each schedule and the number of schedules initiated in the Phase 2 portion of the study. The study will enroll approximately 140 subjects.

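### Appendix H lets some subjects measurable only by free light chain meet the first VGPR criterion at baseline, so unchanged disease can count in the primary ORR

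*Protocol*

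**What the plan says.** **Eligibility.** Protocol 4.1, criterion 1c, allows a third form of measurable disease: "Only for subjects without measurable serum and urine M-protein, serum free light chain: Involved free light chain (FLC) level" of at least 10 mg/dL with an abnormal ratio. Under 1a and 1b, not measurable means serum M-protein below 500 mg/dL and urine M-protein below 200 mg/24 h.

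**VGPR.** Appendix H gives two alternatives. The second is a change: a 90% fall in serum M-component with low urine M-component. The first is a state: "Serum and urine M-protein detectable by immunofixation, but not on electrophoresis".

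**nCR.** The EBMT table also describes a state: "Absence of M-protein on electrophoresis, independent of the immunofixation test status, stable bone disease, and a normal serum calcium concentration". The same row opens by calling this an immunofixation-positive response.

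**PR.** Only this row, among the categories counted in ORR, brings in FLC change: "If the serum and urine M-protein are not measurable, a decrease" of at least 50% "in the difference between involved and uninvolved FLC levels is required in place of the M-protein criteria".

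**Footnote d.** "Response criteria for all categories and subcategories of response except CR and VGPR are applicable only to subjects" with SPEP of at least 1.0 g/dL or UPEP of at least 200 mg per 24 hours. The marker is on the VGPR and PR rows. The nCR row carries only its own table's footnote a.

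**Use.** SAP 7.5.1 counts confirmed sCR, CR, nCR, VGPR and PR in ORR. Protocol 10.2 sets the decision rule: "If at least 12 of the 46 subjects have a best overall response of PR or better", the null hypothesis of 15% or less is rejected.

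**The concern.** A response criterion written as a state works only if the subject was not in that state at entry. For a subject enrolled on M-protein, becoming electrophoresis-negative is a real change. For a subject enrolled on FLC alone, electrophoresis may have been negative from the start, and the disease is then followed by a marker that VGPR bullet 1 never mentions.

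The primary Phase 2 endpoint could therefore credit subjects whose disease has not moved. The cut-off is 12 responders, so a few such cases matter. They would also enter the duration-of-response analysis (SAP 7.5.4), which starts at the first observation of PR or better, and would shorten time to response (Protocol 10.1).

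**Working it through.** **Step 1. Follow one subject through the text.** Take a 1c subject with no M-protein on electrophoresis, M-protein detectable by immunofixation in serum and urine, and a flat FLC difference.

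- Screening: eligible under 1c. VGPR bullet 1 already describes this subject.
- Measurability: footnote d exempts VGPR, so the lack of measurable SPEP or UPEP does not block it.
- Confirmation: Appendix H footnote b asks for two consecutive assessments and no known new or progressive bone lesions. Unchanged disease passes.
- Stable disease: defined as what is left when CR, VGPR, PR and PD are not met, so meeting VGPR rules it out.
- Progression: the FLC limb needs a rise of at least 25% and more than 10 mg/dL. A flat FLC, or a smaller rise, is not PD.
- Safeguards: response is judged by the investigator (Protocol 7.6), and SAP 7.5.1 has no baseline check.

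Read literally, the best overall confirmed response is VGPR, and it counts in ORR.

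**Step 2. The nCR row.** It asks for no change in M-protein or FLC, but adds conditions on bone disease and calcium. Two readings of footnote d compete.

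- Literal: every category except CR and VGPR is confined to measurable SPEP or UPEP. That bars nCR for 1c subjects. It also cancels the PR row's own FLC rule, so a 1c subject with a real 50% FLC fall could not be PR while one with flat FLC could be VGPR.
- By placement: the marker is absent from the nCR row, which sits in a separate EBMT table. Then nCR is open to 1c subjects in the same static way.

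The second reading fits the document better, but the text does not settle it. The VGPR route is open under both.

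**Step 3. Reproduce the plan's figures.** Inputs from Protocol 10.2: n = 46, reject at 12 or more, null 15%, alternative 30%, one-sided 5%. With X ~ Bin(46, p):

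- P(X ≥ 12 | 0.15) = 0.0354
- P(X ≥ 12 | 0.30) = 0.7672, which matches the stated 77%
- A cut-off of 11 would give 0.0745, so 12 is the smallest cut-off within 5%.

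**Step 4. Effect of k unchanged subjects counted as responders.** k is an assumption, because the documents give no figure. With a true ORR of 15% in the other 46 − k subjects, type I error = P(Y ≥ 12 − k), Y ~ Bin(46 − k, 0.15).

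| k | True responders needed | Type I error |
|---|---|---|
| 0 | 12 of 46 | 3.5% |
| 1 | 11 of 45 | 6.5% |
| 2 | 10 of 44 | 11.4% |
| 3 | 9 of 43 | 18.7% |

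If instead each subject has probability f of being such a case, the effective null rate is 0.15 + 0.85f. At f = 2% it is 0.167 and type I error is 7.1%. At f = 5% it is 0.1925 and type I error is 16.1%.

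**The case against.** A reader might infer that every FLC-only subject without M-protein on electrophoresis is an automatic nCR or VGPR. The documents do not support that, for four reasons.

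- VGPR bullet 1 also needs immunofixation-detectable M-protein in serum and urine. Negative electrophoresis alone is not enough.
- Not measurable is not the same as absent. A 1c subject with a visible spike below 500 mg/dL meets neither the VGPR bullet nor nCR at entry.
- nCR also needs a normal calcium and bone disease that stays stable, and footnote d read literally excludes these subjects from it.
- Both categories need two consecutive assessments, so early progression or dropout prevents a count.

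A reader might also infer that the trial's type I error exceeds 5%. That is not shown. It requires at least one subject who meets every condition and whom the investigator scores as a responder despite a flat FLC. Many investigators would not do so, and with k = 0 the design performs as stated.

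These limits stand and narrow the point to a subset. They do not remove it: for that subset no written rule prevents the count, and the rule as written gives VGPR.

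**Conclusion.** The point holds for 1c subjects who are electrophoresis-negative and immunofixation-positive in serum and urine at entry. For them Appendix H allows a confirmed VGPR with no change in disease. Whether nCR offers a second route is unresolved, and the nCR row also contradicts itself on immunofixation.

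The error rates in the table are illustrative. They assume k such subjects are scored as responders and a true ORR of 15% in the rest. One case would take the rule past its 5% level; none would leave it at 3.5%. Because a single case is enough and the correction is cheap, the change should be made.

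**What to change.** State in Appendix H and repeat in SAP 7.5.1:

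1. No response category may be assigned on criteria already met at baseline.
2. Subjects measurable only by FLC count as PR or better only with at least the PR row's 50% fall from baseline in the involved-minus-uninvolved FLC difference, confirmed on two assessments. ORR pools PR and above, so it needs no separate VGPR level for them. If VGPR is reported by category, a level must be set.
3. Footnote d is reworded to allow the PR row's FLC rule, to say whether it governs nCR, and to reconcile its 1.0 g/dL serum threshold with the 500 mg/dL in inclusion 1a. At present, subjects between the two are eligible but not measurable under footnote d.
4. The two conflicting immunofixation phrases in the nCR row are reconciled.

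The summary of changes for Amendment 4 says the primary analysis is complete. The practical step is therefore to list any 1c subject recorded as VGPR or nCR, check the FLC course, and report ORR with the rule applied, labelled as post hoc.

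Cost: wording and a data check. Appendix E footnote b already requires SFLC from all subjects at each response assessment, so no new data are needed. With the rule in force (k = 0) the design keeps 12 of 46, 3.5% type I error and 76.7% power. The observed ORR may be slightly lower.
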